7 STUDY OUTCOMES

7.1 PRIMARY OUTCOMES

The cognitive task will consist of 400 trials. The EEG recorded simultaneously with the task will be analyzed following an established preprocessing pipeline to remove artifacts related to eye movements, eye blinks, heart beats and muscle activity. The oscillation power and phase will be estimated using Morlet wavelet convolution. The primary outcome is phase-amplitude coupling between the stimulated frequencies (measured from EEG), reaction time, and accuracy. Phase amplitude coupling will be calculated using the phase locking value z-corrected based on a boot-strapped null distribution from randomly shifting the amplitude values 1000 times (see Cohen *Analyzing Neural Time Series Data* 2014 for method).

Our primary outcomes:

- Theta-gamma tACS will increase theta-gamma phase amplitude coupling (one-tailed, Student's t-test)
- Delta-beta tACS will increase delta-beta phase amplitude coupling (one-tailed, Student's t-test).
- Theta-gamma tACS will alter behavior (reaction time or accuracy) as a function of set-size (Student's t-test).
- Delta-beta tACS will alter behavior (reaction time or accuracy) as a function of abstraction (Student's t-test).

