7.2 SECONDARY OUTCOMES

The following will be assessed as secondary outcomes

- Brain behavior correlation to account for inter-participant variance. For the significant behavioral findings, we will correlate the strength of phase amplitude coupling during the post-stimulation rest period with the impact on behavior.
- For the significant behavioral findings, brain behavior correlation between the strength of phase amplitude coupling in the baseline session to the behavioral effect of CF-tACS on task performance.

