12.2 STATISTICAL ANALYSIS PLANS

Statistical analyses will be performed to test the null hypothesis indicated in section 2.4 *Study Aims/Hypothesis*.

The cognitive task will consist of 400 trials. The EEG recorded simultaneously with the task will be analyzed following an established preprocessing pipeline to remove artifacts related to eye movements, eye blinks, heart beats and muscle activity. The oscillation power and phase will be estimated using Morlet wavelet convolution. The primary outcome is phase-amplitude coupling between the stimulated frequencies (measured from EEG), reaction time, and accuracy. Phase amplitude coupling will be calculated as the phase locking value corrected for spurious noise using a boot-strapped null distribution (see Cohen Analyzing Neural Time Series Data 2014 for method).

Our primary outcomes and their test are described below:

- Theta-gamma tACS will increase theta-gamma phase amplitude coupling (one-tailed, Student's t-test)
- Delta-beta tACS will increase delta-beta phase amplitude coupling (one-tailed, Student's t-test).
- Theta-gamma tACS will alter behavior (reaction time or accuracy) as a function of set-size relative to sham-tACS (Student's t-test).
- Delta-beta tACS will alter behavior (reaction time or accuracy) as a function of abstraction relative to sham-tACS (Student's t-test).

As exploratory analysis, linear mixed-effects models with BDNF genotype, sex hormone levels, as factors in addition to the variables condition and period will be fit with the rest of the analysis following what is described for primary analysis.

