12.3 SAMPLE SIZE DETERMINATION

Based on the study by Alekseichuk et al 2017 which investigated the effect of CF-tACS on task accuracy and resting state EEG connectivity in 20 healthy participants per crossover arm, we conjecture that our effect size is at least 0.48. With this effect size, our sample size of 24 has power greater than 60% with alpha 0.05. We have improved upon the experimental design in Alekseichuk et al 2017 by personalizing our stimulation frequencies to target the frequencies of peak phase-amplitude coupling during the task. With this methodological improvement, we expect our effect size to increase to 0.6 (see Romei et al. 2016). With this effect size, our sample size has power greater than 85%.

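### Sections 7.1 and 12.2 word each behavioural primary hypothesis as reaction time or accuracy with no deciding measure or adjustment; if either measure suffices, the false-positive rate per hypothesis is about 7–10% against the 0.05 in 12.3

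*Combined protocol and SAP*

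**What the plan says.** The primary outcome is described in the same terms in 7.1 and 12.2: "The primary outcome is phase-amplitude coupling between the stimulated frequencies (measured from EEG), reaction time, and accuracy". Four primary hypotheses follow.

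- Two concern coupling and carry a tail label, for example "Delta-beta tACS will increase delta-beta phase amplitude coupling (one-tailed".
- Two concern behaviour and carry none. In 12.2 the first reads "Theta-gamma tACS will alter behavior (reaction time or accuracy) as a function of set-size relative to sham-tACS"; in 7.1 the second reads "Delta-beta tACS will alter behavior (reaction time or accuracy) as a function of abstraction". Both are to be tested by Student's t-test.

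Neither section ranks reaction time and accuracy, requires both, or adjusts for testing two.

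Section 7.2 makes both secondary brain-behaviour correlations depend on the behavioural result: "For the significant behavioral findings, we will correlate the strength of phase amplitude coupling during the post-stimulation rest period" and "For the significant behavioral findings, brain behavior correlation between the strength of phase amplitude coupling in the baseline session".

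Section 12.3 gives the only alpha and two power bounds. At an effect size of 0.48: "With this effect size, our sample size of 24 has power greater than 60% with alpha 0.05". At 0.6: "With this effect size, our sample size has power greater than 85"%. It mentions accuracy and EEG connectivity only as outcomes of the cited earlier study. It does not assign the bounds to any of this trial's tests, and it gives neither the sidedness nor the type of effect size.

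**The concern.** A hypothesis that can be met by either of two measures, each tested at 0.05, has two chances of a false positive. The plan neither rules this out nor allows for it, so a behavioural primary claim could carry up to about twice the error rate that 12.3 uses. A chance finding would also carry forward, because 7.2 runs its correlations only for behavioural findings that turn out significant.

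The sidedness gap matters for a related reason. The coupling tests are one-tailed by label. The behavioural tests have no label and speak of altering behaviour, which reads most naturally as two-sided, while the alternative hypothesis in 12.1 speaks of improved performance. A reader of 12.3 therefore cannot tell which primary tests have the stated power.

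**Working it through.** **Inputs.** From the documents: n = 24, all in a within-participant crossover (section 4); alpha 0.05 and effect sizes 0.48 and 0.6 (12.3). Assumed: the effect sizes are standardised paired differences d; the correlation between the reaction-time and accuracy contrasts lies between -0.9 and 0.9.

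**Step 1: the power bounds in 12.3.** For a paired t-test, df = 23 and the noncentrality is d × √24, which is 2.352 at d = 0.48 and 2.939 at d = 0.6. Power is the noncentral-t probability beyond the critical value: 1.714 for one-sided 0.05, 2.069 for two-sided 0.05, 2.398 for two-sided 0.025.

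| Test | d = 0.48 | d = 0.6 |
|---|---|---|
| Bound stated in 12.3 | above 60% | above 85% |
| One-sided 0.05 | 73.8% | 88.6% |
| Two-sided 0.05, one measure | 61.5% | 80.4% |
| Two-sided 0.025 (first Holm step), one measure | 49.3% | 70.4% |

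Both bounds are reproduced by a one-tailed paired test. Tested two-sided, one measure meets the first bound and misses the second.

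**Step 2: false-positive rate if either measure suffices.** For independent measures it is 1 - 0.95² = 9.75%. For correlated measures, two paired t-tests with n = 24 and no effect were simulated, each at 0.05.

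| Correlation | Two-sided | One-sided, improvement direction |
|---|---|---|
| +0.9 | 7.1% | 6.8% |
| +0.7 | 8.4% | 8.1% |
| +0.5 | 9.1% | 8.8% |
| 0 | 9.75% | 9.75% |
| -0.5 | 9.1% | 9.9% |
| -0.9 | 7.1% | 10.0% |

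The rate is about 7–10% whichever sidedness was meant. It approaches 5% only when the measures are almost perfectly correlated; at 0.95 it is 6.4% two-sided.

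**Step 3: after the change.** One named measure has a 5% rate by construction. With Holm, a false rejection of either measure needs the smaller p-value to be at or below 0.025. For independent measures the rate is 1 - 0.975² = 4.9%. Over correlations from -0.9 to 0.9 it is 3.6–4.9% two-sided and 3.5–5.0% one-sided.

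**Step 4: power under two-sided Holm.** The 49.3% and 70.4% in step 1 are lower limits for one measure, because the second Holm step tests at 0.05. They are not power for the hypothesis. If both measures carry the stated effect, the chance of at least one rejection, for correlations 0.9 to 0, is about 57–74% at 0.48 and 77–91% at 0.6.

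**The case against.** The documents never state that either measure is enough. Reaction time and accuracy are listed as separate parts of the primary outcome, and 7.2 refers to significant behavioural findings in the plural, which also fits reporting each measure as its own claim. On that reading 0.05 per test agrees with 12.3. This stands, and it is why the 7–10% is conditional. A reader might infer that the plan definitely runs its behavioural hypotheses at that rate; the text does not go that far. What remains on the separate-claims reading is that nothing says what is concluded when the two measures disagree, for instance faster but less accurate responses.

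On power, a reader might infer that the 85% bound in 12.3 is wrong. It is not shown to be: one-tailed paired tests meet both bounds, and two of the four primary tests are labelled one-tailed. There is a further point in the plan's favour. If either measure suffices unadjusted and both carry the effect, the chance of at least one two-sided rejection is about 85.5–96% at 0.6 and 69–85% at 0.48 (correlations 0.9 to 0), so both bounds hold for the hypothesis. That power is bought with the inflated error rate, and it falls towards the single-measure figure if only one measure responds.

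Finally, this is a pilot. Section 2.4 sets out to characterise effects, generate hypotheses and obtain estimates, and no go/no-go rule hangs on these tests. That lowers the weight. It does not remove the point, because 7.1 and 12.2 call these outcomes primary and name tests for them, and 12.3 attaches an alpha.

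**Conclusion.** The point holds conditionally, at minor-to-moderate weight. If either measure at 0.05 confirms a behavioural hypothesis, its false-positive rate is about 7–10% rather than 5%, for correlations between -0.9 and 0.9 and for one-sided or two-sided tests. The correlation range is an assumption.

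The power issue is a reporting gap. On the paired-difference assumption, the 85% bound fits the one-tailed coupling tests but not one behavioural measure tested two-sided (80.4%), and 12.3 does not say which it means. A reader might also infer a demand for error control across all four primary hypotheses, or for a larger sample. Neither is claimed: the point is confined to the two measures within each behavioural hypothesis.

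**What to change.** - **7.1 and 12.2:** for each behavioural hypothesis, name reaction time or accuracy as the deciding measure, or apply Holm across the two at 0.05. State whether the test is one-sided or two-sided and, if one-sided, the expected direction for each measure.
- **12.3:** say whether 0.48 and 0.6 are standardised paired differences and which test each bound describes. If they are, give 74% and 89% for the one-tailed coupling tests. For one named behavioural measure give 61.5% and 80% if two-sided, or 74% and 89% if one-sided, and do not state the 85% bound for the two-sided case.
- **If two-sided Holm is chosen:** give 49% and 70% as lower limits for one measure, and label any at-least-one-rejection figure with its assumption that both measures carry the effect.

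The cost is wording only, with no more participants. The downside is that one measure becomes secondary, or the stated power becomes less favourable than now.

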We will be collecting a saliva sample at the first session. This sample will be used to test for a single nucleotide polymorphism in the BDNF gene whose presence may have an influence on effectiveness of brain stimulation. Within the central nervous system, BDNF regulates survival, proliferation, and synaptic growth as well as directly influences synaptic plasticity in the adult human brain (Antal et al., 2010). Egan et al. (2003) demonstrated that Val66Met, a single nucleotide in the BDNF gene, has function consequences in healthy humans, including decreased episodic memory and hippocampal inducing a reduction in recall capacity. This polymorphism is common in over one third of the Caucasian population (65% Val66Val to 35% Val66MET) (Pezawas et al, 2004; Hariri and Weinberger, 2003). Kleim et al. (2006) found that individuals with the Val/Val polymorphism respond to tDCS and transcranial magnetic stimulation (TMS) treatments with expected change, whereas, individuals expressing Val/MET allele do not. These authors indicate the difference to be caused by the impairment in synaptic plasticity caused by the Val/MET allele. These findings suggest that individual efficacy of treatments using brain stimulation may be partially genetically predetermined and should be taken into account when performing such procedures. Accordingly, we will conduct genotyping of all participants in this study in order to assess BDNF status.

In addition to BDNF, we will be assessing sex hormone levels in our participants before stimulation. Cortical excitability has been shown to depend on the phase of the menstrual cycle in women (Smith et al. 1999, Badawy et

al. 2013, Walpurger et al. 2004). This effect may be mediated by sex hormones (e.g., estradiol, progesterone, testosterone, androstenedione). To account for the different levels of sex hormones in participants when they arrive for the experimental sessions, we will collect saliva for assessing levels of estradiol, progesterone and testosterone. In addition, we will ask women information on birth control use and the best guess-estimate of first day of last menstrual cycle.

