4 BASIC STUDY DESIGN

The design for this study is a pilot, randomized, double-blind, sham-controlled, crossover clinical trial which will be used to demonstrate feasibility and collect effectiveness data for further refinement of CF-tACS approach and for the subsequent design of a follow-up, multi-site, large scale study. We are seeking 24 healthy participants, both male and female, between the ages of 18-35. All women of child-bearing potential (defined as menstruating women of all ages) will be asked to take a pregnancy test during the initial session in order to determine eligibility for the study. We estimate 2 months to complete study enrollment.

The experimental design is a 3-treatment, 3-period, 3-sequence crossover with a 1 week washout interval between periods. N=24 participants will be enrolled and allocated by stratified randomization to six treatment sequences, S-At-Ad, S-Ad-At, At-S-Ad, At-Ad-S, Ad-S-At, Ad-At-S. S refers to Sham Regimen which is 40 minutes of sham CF-tACS, At refers to Active Theta-Gamma Frequency Regimen which is 40 minutes of verum CF-tACS, and Ad refers to Active Delta-Beta Frequency Regimen which is 40 minutes of verum CF-tACS.

Participants will be randomly assigned to one of 6 sequences on the first visit.

Sham treatment will include 10 seconds of ramp-in to 1 minute of CF-tACS with a ramp-out of 10 seconds for a total of 80 seconds of stimulation. The 80 seconds of stimulation serves to desensitize the scalp beyond which participants are generally not able to tell apart the presence or absence of stimulation. This strategy has been described in previous studies using tACS (Alekseichuk et al. 2017; Mellin et al. 2018). Verum CF-tACS will have a 10 second ramp-in and ramp-out with 5 minutes of stimulation, for 8 separate blocks with a minimum 3 minute break between each block, for a total of 2560 seconds of stimulation. Stimulation waveform is coupled frequency with a low frequency component and brief high frequency component on each cycle with maximum amplitude of 2 mA.

Eligible participants will have a total of 4 visits, each lasting approximately 3 hours and separated by at least 1 week. Total participation will include about 12 hours over the course of four weeks. All time estimates take into consideration breaks and time variance in administration.

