5.2 STIMULATION SESSIONS

Participants will undergo four sessions with the same procedure; the only change will be the stimulation condition. In the initial session, participants will have the procedure explained and reminded of their expectations and rights (informed consent). After obtaining consent, a urine drug test and pregnancy screening will be administered. Sessions 2, 3, and 4 will be the same as session 1, except there will be no CF-tACS stimulation during session 1.

5.4.1 SESSION 1

In the initial session, participants will be explained the procedure and reminded of their expectations and rights (informed consent). After obtaining consent, a urine drug test and pregnancy screening will be administered.

- Preparation - Once a negative pregnancy test and negative drug test are confirmed, the stimulation electrodes, EEG net, ECG electrodes and respiration belt will be applied.
- Questionnaires - The participant will fill out a series of questionnaires pertaining to self-reported handedness, affect, behavioral traits and sleep quality.
- Saliva collection - Saliva will be collected for BDNF genotyping and sex hormone level measurement.
- Resting state EEG – Participant will be asked to relax with eyes open and EEG will be collected simultaneously
- Practice cognitive tasks - The participant will perform a shortened version of the cognitive tasks as practice from which baseline performance will be assessed.

· Following the practice, the participant will receive 40 minutes of either verum CF-tACS or sham CF-tACS stimulation, depending on the randomized condition. During the stimulation, the following procedures will be followed

A. Cognitive Control Task – Participant will perform a cognitive control task for 5 minutes. CF-tACS will be delivered during these 5 minutes. There will be no CF-tACS during session 1.

B. Resting state EEG - Participant will be asked to relax with eyes open and EEG will be collected simultaneously for 3 minutes. There will be no CF-tACS during this time. Subject are allowed to take more (but not less) than 3 minutes of rest if desired.

- Repeat steps A and B 8 times until all conditions of the Cognitive Control Task are finished

Following the end of stimulation,

- Electrodes and net will be removed and participant can wash their hair and face

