7.3 EXPLORATORY OUTCOMES

Additionally, the following exploratory measures will be assessed

- Modulation in spectral power in other frequency bands (1 – 4 Hz; 8 – 12 Hz; 12 – 30 Hz; 30 – 50 Hz) of CF-tACS
- Coherence between distant regions of the brain in the slower frequency of the CF-tACS coupled pair (delta and theta)
- Hormone level and BDNF as covariates in analysis of differences in spectral power
- Self-reported anxiety, affect and sleep quality as covariates in the analysis of differences in spectral power

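### The exploratory mixed model pools men and women and includes sex-hormone levels without a sex term, so its hormone coefficients are confounded with sex

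*Combined protocol and SAP*

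**What the plan says.** Section 4 sets the population: "We are seeking 24 healthy participants, both male and female, between the ages of 18-35". It gives no planned number of each sex. It refers to stratified randomization but does not name the stratification factor.

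Section 12.2 lists the terms of the exploratory model: "linear mixed-effects models with BDNF genotype, sex hormone levels, as factors in addition to the variables condition and period will be fit". Section 7.3 has two covariate entries, "Hormone level and BDNF as covariates in analysis of differences in spectral power" and "Self-reported anxiety, affect and sleep quality as covariates in the analysis of differences in spectral power". Sex is in none of these lists. No section fits the model by sex or standardises hormone levels within sex. Section 12.2 does not say whether hormones enter only as main effects or also in interaction with condition.

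Section 2.1 explains why hormones are measured. It states that "Cortical excitability has been shown to depend on the phase of the menstrual cycle in women". It gives the purpose of the samples as "To account for the different levels of sex hormones in participants when they arrive for the experimental sessions" and the assays as "we will collect saliva for assessing levels of estradiol, progesterone and testosterone". Women are also to be asked about birth control and the start of their last cycle. No analysis section uses that information, and Appendix A does not list it.

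On timing, the Session 1 procedures under section 5.2 say "Saliva will be collected for BDNF genotyping and sex hormone level measurement", and Appendix A marks saliva at Session 1 only.

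**The concern.** Levels of sex hormones can be expected to differ between men and women. If one slope is fitted across both sexes with no sex term, part of the hormone variation is simply the male-female contrast. Any sex difference in the outcome then loads on the hormone coefficient.

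This matters because of what the estimates are for. Under Aims 2 and 3 in section 2.4, the pilot is to generate hypotheses and supply estimates for a larger study. A sex difference reported as a hormone effect would point that study at the wrong mechanism. The mismatch is sharper because section 2.1 motivates the measurement by variation among women over the cycle, which a pooled slope does not isolate.

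**Working it through.** The plan states no figure for this point, so there is none to reproduce. The check asks what the omitted term can do.

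**Inputs.** From the documents: N = 24, both sexes, and the model terms in 12.2 and 7.3. Assumed, because the documents give none of them: the share of women *f*; the male-female hormone difference *D* in within-sex SDs; the sex difference in the outcome *g* in within-sex SDs; and a true within-sex hormone slope of 0.

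**Step 1: algebra for one hormone.**

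- Share of pooled hormone variance that is sex = f(1−f)D² / [1 + f(1−f)D²].
- Expected pooled slope when the true slope is 0 ≈ g·f(1−f)D / [1 + f(1−f)D²].

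With f = 0.5, D = 2, g = 1, the share is 0.25×4/(1+1) = 50% and the slope is 0.25×2/2 = 0.25. Simulation gave a mean slope of 0.259 without sex and −0.003 with sex. If g = 0 the slope is 0 whatever D is.

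**Step 2: false-positive rate for a null hormone effect.** Participant-level regression, 12 men and 12 women, two-sided 5%, 20,000 runs per setting:

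| D | Share that is sex, f = 0.5 | Share, f = 0.25 | No sex term, g = 0 | g = 0.5 | g = 1 |
|---|---|---|---|---|---|
| 0 | 0% | 0% | 5% | 5% | 5% |
| 0.5 | 6% | 4.5% | 5% | 6% | 8% |
| 1 | 20% | 16% | 5% | 8% | 16% |
| 2 | 50% | 43% | 5% | 13% | 34% |
| 3 | 69% | 63% | 5% | 16% | 47% |

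With sex in the model the rate is 4.6% to 5.2% in every cell.

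**Step 3: the same on a ratio scale.** Let r be the between-sex ratio of a hormone and CV its within-sex coefficient of variation, with equal numbers of each sex. Share of log variance = (ln r/2)² / [(ln r/2)² + ln(1+CV²)].

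- CV 40%, ln(1.16) = 0.148. For r = 2, 0.120/(0.120+0.148) = 45%. For r = 3 and 5, 67% and 81%.
- CV 100%, ln(2) = 0.693. For r = 2, 0.120/(0.120+0.693) = 15%. For r = 3 and 5, 30% and 48%.

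At CV 40% (4,000 data sets per setting, 12 of each sex), the false-positive rates for r = 2, 3, 5 are 12.4%, 16.0%, 17.4% with a 0.5 SD sex effect and 22.2%, 32.4%, 38.9% with 0.8 SD. With sex in the model they are 4.5% to 5.0%. With 16 women and 8 men the rates without sex are 11–17% and 19–35%, so equal numbers are not essential.

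At CV 100%, D = ln r/√0.693 = 0.83, 1.32, 1.93. These fall between the D = 0.5 and D = 2 rows above: roughly 6% to 13% for g = 0.5 and 8% to 34% for g = 1.

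**Step 4: timing.** If saliva is taken only at Session 1, the hormone value is constant within a participant, so its coefficient rests wholly on differences between people, where sex acts. If it were taken at every session, as the purpose stated in 2.1 could suggest, the within-person part could not be sex, but the between-person part would still be confounded.

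**Limits.** The calculation takes one hormone at a time, without BDNF genotype, at participant level.

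**The case against.** Several counter-arguments have force.

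- **Size.** A reader might infer that the hormone effects will largely re-express sex differences. The documents do not support that. Sex makes up half or more of a hormone's variance only at about D = 2 or above with equal numbers, and at a CV of 100% it stays below half even at a fivefold ratio. The answer may differ among the three hormones.
- **A sex effect is needed.** With no sex effect on the outcome the error rate stays at 5%. If the analysed quantity is a within-person difference between conditions, a constant sex difference cancels. Only a sex-by-condition difference could then distort a hormone coefficient. That stands, and it is why the moderator case has to be treated separately.
- **Covariates only.** Section 7.3 calls hormones covariates. As pure adjustment variables they may absorb sex-related variance harmlessly, and nothing says their coefficients will be read causally. This does not settle the matter, because Aims 2 and 3 use exploratory estimates to form hypotheses and plan the next study.
- **Stratification.** The unnamed stratification factor might be sex. That would balance treatment sequences but would not separate hormone from sex across participants.
- **Primary results.** A reader might infer that these are compromised. They are not: the primary t-tests contain no hormone term, and a between-person main effect does not bias within-person condition contrasts in complete, balanced data.

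**Conclusion.** The omission is in the text: the sexes are pooled, sex-hormone levels are in the model and sex is not. The between-person hormone coefficients are therefore confounded with sex and cannot be interpreted as hormonal. Where hormones are fitted as moderators of the stimulation effect, the same holds for sex-by-condition differences.

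How much distortion results cannot be settled from the documents. It depends on the hormone, its within-sex spread and the effect of sex on the outcome. The computed error rates show what is possible under assumed values and are not predictions for this trial. What does not depend on those values is that including sex restores the nominal rate in every setting examined. Severity is low: this is one exploratory analysis in a 24-person pilot.

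**What to change.** In sections 12.2 and 7.3, add sex as a factor. State whether hormone by condition will be fitted and, if so, add sex by condition as well. The hormone slopes are then within-sex slopes, and only those should be interpreted.

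The cost is one degree of freedom for sex, plus two for sex by condition with three conditions. No new participants or assays are needed: demographics are taken at telephone screening (section 6.1). The hormone slopes also lose precision. At equal numbers and equal residual variance, the variance inflation from adding sex is 1/(1 − share): 1.25, 2.0 and 3.25 at D = 1, 2 and 3. Standard errors are then about 1.1, 1.4 and 1.8 times as large (square roots). The precision given up came from the confounded male-female contrast.

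This removes the sex confounding but not every difficulty. If saliva is collected at Session 1 only, which has no stimulation, no model term recovers cycle phase at the later stimulation sessions. Section 2.1 and Appendix A should be made to agree on when hormones are sampled. A women-only model with contraceptive use is optional; it would be imprecise at this sample size, and collection of that item should first be confirmed because Appendix A omits it.
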